6.2 Timing of Analyses

One interim study team and Safety Monitoring Committee (SMC) safety and PK review will occur after Part A 6 participants in Group 2 (severe renal impairment and ESRD, not on dialysis) and Group 1A their matched controls are enrolled and completed follow-up through Day 12 (Visit 02). The interim safety and PK review will present data by group, including AEs, SAEs, clinical laboratory tests, vital signs, and 12-lead ECG, and PK analysis of pretomanid. Cumulative data for all participants enrolled will be included in the safety and PK reviews. The interim safety and PK reviews will not include any statistical hypothesis testing.

The final analysis will be performed after database lock.

6.3 Analysis Populations

6.3.1 Safety Analysis Population

The safety analysis population set will include all participants who receive any amount of study product.

6.3.2 Pharmacokinetic Analysis Population

The PK analysis population will consist of participants who received pretomanid and provided sufficient bioanalytical assessment results to calculate reliable estimates of the PK parameters. Any participants or data values excluded from PK analyses will be identified, along with their reason for exclusion, in the clinical study report.

6.3.2.1 PK Plasma Analysis Subset

The PK plasma analysis subset will consist of all participants with sufficient plasma PK data available to estimate the plasma PK parameters listed in [Section 4.5.1](#). The PK plasma analysis subset may be used for post-hoc sensitivity analyses if the PK analysis population is different from the PK plasma analysis subset (i.e. when a participant has estimable plasma parameters but is excluded from the PK analysis population due to challenges with their urine PK data).

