10.5.1.2 PK Analysis Population

The PK analysis population will consist of participants who received pretomanid and provided sufficient bioanalytical assessment results to calculate reliable estimates of the PK parameters. Any participants or data values excluded from PK analyses will be identified, along with their reason for exclusion, in the clinical study report.

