6.3.2.2 PK Urine Analysis Subset

The PK urine analysis subset will consist of all participants with sufficient urine PK data available to estimate the urine PK parameters listed in [Section 4.5.1](#). The PK urine analysis subset may be used for post-hoc sensitivity analyses if the PK analysis population is different from the PK urine analysis subset (i.e. when a participant has estimable urine parameters but is excluded from the PK analysis population due to challenges with their plasma PK data).

Reasons for exclusion from an analysis population will be summarized in [Table 8](#) by impairment group. Individual participant listing of exclusion reasons is also provided in [Listing 6](#).

A tabular listing of all participants, visits, and observations excluded from the efficacy analysis will be provided in the CSR (Listing 16.2.3).

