9 SAFETY EVALUATION

All summaries and analysis of safety data will be presented for the Safety Analysis Population. Safety summaries will be presented by renal impairment group and overall.

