10 PHARMACOKINETICS

PK analyses will be performed using NCA. PK concentrations and noncompartmental parameters will be summarized by renal impairment group. Statistics include the arithmetic mean, median, SD, GM, CV, min, and max. PK parameters of exposure (AUC_{last}, AUC_∞, and C_{max}) will be compared between impairment groups using ANOVA models with or without random effects. T_{max} will be compared using 90% confidence intervals calculated using the inverted rank score method. Concentrations below the quantitation limit (BQL) prior to first measurable concentration will be imputed as zero. The first BQL concentration reported in the plasma concentrations after the last measurable concentration may be imputed for the purpose of parameter estimation as the LLOQ divided by 2 only if 1) needed to estimate λ_z, 2) all other λ_z estimation criteria are met, and 3) if a visual predictive check of the imputed value appears to be consistent with the observed elimination trend. All other BQL samples will be treated as missing. Imputed concentration values will only be used for plasma parameter estimation by NCA and not included in concentration summaries, however, imputed BQL values will be indicated by imputation method in listings with methods clarified in the footnote and denoted in figures.

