10.2.2 Pharmacokinetic Parameters

10.2.2.1 Plasma Pharmacokinetic Parameters

NCA PK parameters will be calculated using the actual post-dose time. Samples with concentrations greater than the LLOQ will be considered for the estimation of λ_z . Imputing the first BQL concentration following the last concentration greater than LLOQ to LLOQ divided by 2 will be considered on a participant-by-participant basis for participants where the λ_z acceptance criteria are not met by the observed data greater than the LLOQ. λ_z will be computed from the log-transformed concentration data. The correlation between time and concentration at the time points used to estimate λ_z should be sufficiently high (adjusted- $R^2 > 0.9$) for λ_z . Additionally a minimum of three concentrations in the terminal elimination phase will be used for the calculation of λ_z . All concentrations used to calculate λ_z must come from samples taken at or after T_{max} . The concentrations used to calculate λ_z along with the number of concentrations used for the calculation will be included in the participant listing ([Listing 22](#)).

The plasma AUC will be computed using the linear-up log-down (linear-log) trapezoidal method in Phoenix WinNonlin (Certara, Radnor, PA).

All plasma PK parameters will also be summarized by renal impairment group using descriptive statistics ([Table 84](#) through [Table 87](#)). Additionally, participant-level PK parameters will be presented in the tables in the final report.

The following parameters will be estimated: C_{max} , T_{max} , AUC_{last} , AUC_{∞} , % AUC_{ex} , $t_{1/2}$, λ_z , CL/F , and V_d/F .

See Section 3.3.1 for parameter definitions.

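### Urine problems can remove valid plasma AUC and Cmax values from the primary PK comparison, because no population is named for it and the plasma-evaluable set is left to optional post-hoc use

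*SAP*

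**What the plan says.** SAP 6.3.2 defines one PK analysis population: dosed participants who "provided sufficient bioanalytical assessment results to calculate reliable estimates of the PK parameters". Protocol 10.5.1.2 has the same single definition, "participants who received pretomanid and provided sufficient bioanalytical assessment results to calculate reliable estimates of the PK parameters". Neither separates plasma from urine.

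SAP 6.3.2.1 then defines a plasma subset and explains when it would differ from the main population: "when a participant has estimable plasma parameters but is excluded from the PK analysis population due to challenges with their urine PK data". Its role is limited: "The PK plasma analysis subset may be used for post-hoc sensitivity analyses". SAP 6.3.2.2 mirrors this for urine: "The PK urine analysis subset may be used for post-hoc sensitivity analyses".

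For safety the SAP assigns a population outright: "All summaries and analysis of safety data will be presented for the Safety Analysis Population". For pharmacokinetics it does not. SAP 10 says that AUClast, AUCinf and Cmax "will be compared between impairment groups using ANOVA models with or without random effects". SAP 10.2.2.1 says "All plasma PK parameters will also be summarized by renal impairment group using descriptive statistics". SAP 10.2.3 gives the model and the fold differences, and Protocol 10.1 gives the Part A AUC ratio. None of these names an analysis set. In SAP Appendix 1, the Table 5 shell lists separate PK, PK Plasma and PK Urine populations without linking any to an analysis, and the only table note on the Table 93 fold-change shell identifies the comparator.

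**The concern.** By the definitions in SAP 3.3.1, AUC and Cmax come from plasma concentrations alone. Of the listed parameters, only renal clearance needs both matrices. A urine problem is therefore no reason to discard a plasma AUC.

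If the plasma-evaluable set is only a sensitivity set, the main comparison must by implication use the PK analysis population, and SAP 6.3.2.1 says urine problems can remove someone from that. If instead no set is assigned, the primary set could be chosen after the data are seen. Either way, the primary exposure comparison, with six participants per group, lacks a fixed and appropriate population.

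The route is plausible, though its frequency is unknown. Protocol 2.2.1 expects less than 1% of unmetabolized drug in urine, SAP 10.2.2.2 uses only urine concentrations above the LLOQ, and the 48 to 96 hour collections may be done at home. Protocol 5.2.2 replaces a participant who misses a PK blood draw for lack of venous access, but lists no such trigger for urine.

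**Working it through.** **Inputs.** Six per group, a planning CV of 20%, prior-study CVs of 16% to 33%, a true ratio of 2.0 and a threshold of 1.5 (Protocol 10.2, SAP 5). Assumption: one or two Group 2 participants are lost to urine problems unrelated to their AUC, and all controls are kept. The documents give no rate. For orientation, if each participant had a 5%, 10% or 20% chance of loss, the chance of losing at least one of six would be 1 − 0.95⁶ = 26%, 1 − 0.90⁶ = 47% or 1 − 0.80⁶ = 74%.

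**Model.** AUC is log-normal, with σ = √ln(1 + CV²) = 0.159, 0.198 and 0.322 for CVs of 16%, 20% and 33%.

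**The plan's own figures (CV 20%).**
- Six versus six: SE = 0.198 × √(1/6 + 1/6) = 0.1143. P(observed ratio ≥ 1.5) = Φ(ln(2/1.5)/0.1143) = 99.4%, matching the stated >99%.
- P(90% CI lower limit ≥ 1.5), by noncentral t with noncentrality ln(2/1.5)/SE: six pairs (df 5) give 69.7%, matching the stated 70%. An unpaired analysis (df 10) gives 75.7%.
- The stated interval (1.70, 2.35) reproduces with 6 versus 18 controls: SE 0.0934, df 22.

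**Part A with n = 6, 5 or 4 in Group 2 and 6 controls (unpaired).** SE = σ√(1/n + 1/6), df = n + 4, CI = 2·exp(±t₀.₉₅·SE). At CV 20%:

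| n | SE | t₀.₉₅ | 90% CI at observed 2.0 | Upper/lower | P(lower ≥ 1.5), true 2.0 | P(observed ≥ 1.5), true 2.0 | Same, true 1.7 |
|---|---|---|---|---|---|---|---|
| 6 | 0.1143 | 1.812 | 1.63–2.46 | 1.51 | 75.7% | 99.4% | 86.3% |
| 5 | 0.1199 | 1.833 | 1.61–2.49 | 1.55 | 71.5% | 99.2% | 85.2% |
| 4 | 0.1278 | 1.860 | 1.58–2.54 | 1.61 | 65.9% | 98.8% | 83.6% |

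At a true ratio of 1.5 the gate probability is 50% whatever n is. The lower-limit probability for n = 6, 5 and 4 is 90%, 87% and 82% at CV 16%, and 42%, 39% and 35% at CV 33%.

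**If whole pairs are lost (paired, CV 20%).** Six, five and four pairs give 69.7%, 59.9% and 47.7%. This is a worst case, since the mixed model in SAP 10.2.3 can retain an unmatched control.

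**Final analysis if Part B runs.** The SAP 10.2.3 code has one control reference level, so all 18 controls are pooled. With SE = σ√(1/n + 1/18) and df = n + 6 + 6 + 18 − 4 = 32, 31 and 30, the intervals are (1.71, 2.34), (1.69, 2.37) and (1.66, 2.41). The upper-to-lower ratio goes from 1.37 to 1.40 or 1.45, and P(lower limit ≥ 1.5) is 91%, 88% and 82%.

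**The case against.** The strongest reply is that the harm rests on inference. The population definitions do not themselves require urine data; the exclusion route appears only in a parenthesis explaining when a sensitivity analysis might be wanted. SAP 10.2.3 drops the matching effect when no matched participants have PK parameters, which fits a parameter-by-parameter reading. SAP 6.3.2 also allows single data values to be excluded, so a urine problem need not remove the whole participant, and because the urine parameters run from 0 to t, a missed late collection may only shorten t. This shows that the trigger may be rare, but none of it assigns a population.

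For Part A the inference is weaker still. Protocol 10.4.1 and SAP 6.2 and 6.6 put cumulative data for all enrolled participants into the interim review, and Protocol 10.1 refers to a PK Manual that was not available for this review. That is a fair limit, although those sections do not define the set for the AUC ratio.

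It can also be said that the effect is small and would be visible. That stands: SAP 6.5 expects little missing data, exclusions and reasons will be reported, and participant-level parameters will be in the report tables. Visibility does not settle which result is primary. Finally, the CI lower limit is not the gate. Protocol 10.1 says only that the interval will be considered.

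**Conclusion.** The concern holds. SAP 6.3.2.1 states the exclusion route and confines the plasma-evaluable set to optional post-hoc use, and nothing elsewhere names the population for the plasma comparison. The subset label is also inconsistent, since the plasma subset as described can contain people outside the PK analysis population.

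The consequence is mainly lost precision. Under the stated assumption of one or two urine-only losses in Group 2 at CV 20%, the Part A lower-limit probability falls by about 4 or 10 percentage points unpaired (75.7% to 71.5% or 65.9%), and by more if matched controls are lost too. The observed-50% gate moves by less than one point at a true ratio of 2.0 and by under three points at 1.7. No bias is demonstrated. That the PK analysis population is the default remains an inference, weaker for Part A. This is a cheap improvement that should be made; it does not threaten the design.

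**What to change.** - In SAP 6.3.2 and 10.2.3, name the plasma-evaluable set as primary for AUClast, AUCinf, Cmax and Tmax, including the Part A AUC ratio and the fold-change table. Define it as dosed participants with sufficient plasma data for a reliable estimate of that parameter and analyte, regardless of urine data.
- Use the urine-evaluable set for the amount and percentage of dose excreted, and require both matrices only for renal clearance.
- Replace the optional post-hoc wording in SAP 6.3.2.1 and 6.3.2.2.
- Add the population to the notes of the plasma parameter and fold-change shells.
- Clarify Protocol 10.5.1.2 to match, state that the interim PK review uses the same plasma set, and check this against the PK Manual.

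The reliability condition and the existing exclusion and replacement rules stay as they are. The cost is text only, with no change to data collection. The one drawback is that N may differ between plasma and urine tables and between parameters, which table notes can explain.

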6.3.2.2 PK Urine Analysis Subset

The PK urine analysis subset will consist of all participants with sufficient urine PK data available to estimate the urine PK parameters listed in [Section 4.5.1](#). The PK urine analysis subset may be used for post-hoc sensitivity analyses if the PK analysis population is different from the PK urine analysis subset (i.e. when a participant has estimable urine parameters but is excluded from the PK analysis population due to challenges with their plasma PK data).

Reasons for exclusion from an analysis population will be summarized in [Table 8](#) by impairment group. Individual participant listing of exclusion reasons is also provided in [Listing 6](#).

A tabular listing of all participants, visits, and observations excluded from the efficacy analysis will be provided in the CSR (Listing 16.2.3).

6.4 Covariates and Subgroups

The protocol does not define any formal subgroup analysis and the study is not powered to perform subgroup analyses.

6.5 Missing Data

All attempts will be made to collect all data per protocol. As missing data are expected to be minimal, no imputation or other missing data methods will be performed for missing values other than for partial or missing dates where complete dates are required to flag data as treatment emergent or concomitant with treatment. Partial or missing start and end dates for AEs and concomitant medications will be imputed such that if the missing part of the date causes ambiguity in the temporal relationship to treatment, it will be assumed to be treatment emergent or concomitant. Specifically, dates will be imputed as follows:

Partial and missing start dates

- Dates with missing day only will be imputed as the first of the month unless the month and year are the same as the month and year of the study medication administration date, in which case missing day will be imputed as the day the participant received study medication unless the end date is on or before the date of study medication administration in which case it will be imputed as the first of the month the end date was reported, or the month prior if the end date is the first of the month.
- Dates with both day and month missing will be imputed as 01JAN unless the year is the same as the year of the study medication administration, in which case the missing day and month will be imputed

as the dose day and month the participant received study medication unless the end date is on or before the date of study medication administration in which case it will be imputed as 01JAN of the year the end date was reported, or 01DEC of the year prior if the end date is the first of the year.

- Completely missing dates will be imputed as the date of study medication administration unless the end date is on or before the date of study medication administration, in which case the missing date will be imputed as 01JAN of the same year as the end date was reported, or 01DEC of the year prior if the end date is the first of the year.

Partial and missing end dates

- Dates with missing day only will be imputed as the last of the month.
- Dates with both day and month missing will be imputed as 31DEC unless the year is the same as the year of the study medication administration, in which case the missing day and month will be imputed as the day and month of the participant's last study visit.
- Completely missing dates will be imputed as the date of the participant's last study visit.
- If the status is missing or it is indicated as ongoing then the date will not be imputed unless a death date is available, in which case the missing date will be imputed as the death date.
 - If the imputed date is after the date of death, the date will be set equal to the date of death.

Original dates as reported will be displayed in listings and the imputed dates will be used for derivations only, such as study day and treatment-emergence status.

Any data point that appears to be erroneous or inexplicable based on clinical judgment will be investigated as a possible outlier and may be excluded from analysis.

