8 ASSESSMENT OF SAFETY

8.1 Assessing and Recording Safety Parameters

Safety will be assessed by the frequency and severity of the following:

1. SAEs ([Section 8.1.2](#)) occurring from the time of the study product administration through Visit 03, Day 85+7 days.
2. Adverse Events occurring from the time of the first study product administration (Visit 01A) through Visit 02, Day 12 ± 2 days.
3. Clinical safety laboratory AEs occurring from the time of the first study product administration (Visit 01A) through Visit 02 Day 12 ± 2 days. Parameters to be evaluated include a Hgb, AST, ALT, total bilirubin, BUN, serum creatinine, eGFR, and serum potassium and magnesium.

All AEs/SAEs will be followed until resolution.

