9.3 Adverse Events

An AE is defined as any untoward medical occurrence in a clinical study participant administered a medicinal product, which does not necessarily have a causal relationship with this treatment. An AE can therefore be any unfavorable or unintended sign (including an abnormal laboratory finding), symptom, or disease temporally associated with the use of a medicinal (investigational) product, whether or not it is related to the medicinal (investigational) product. This includes exacerbation of a pre-existing condition or events, intercurrent illnesses, drug interaction or the significant worsening of the indication under investigation that is not recorded elsewhere in the eCRF under specific efficacy assessments. Anticipated fluctuations of pre-existing conditions, including the condition under study, that do not represent a clinically significant exacerbation or worsening need not be considered AEs.

It is the responsibility of the Investigator to document all AEs that occur during the study. AEs must be reported on the appropriate page(s) of the eCRF. All AEs will be coded using the MedDRA dictionary Version 27.0 or higher.

TEAEs are defined as any event that occurs or worsens on or after the day that study treatment initiated. AEs recorded in the eCRF which began prior to treatment will not be included in the summary tables but will be included in the AE data listings ([Listing 9](#)).

The severity of AEs will be graded according to National Cancer Institute (NCI) Common Terminology Criteria for Adverse Events (CTCAE) Version 5.0. The severity of the AE should be the maximum over the course of the AE. For AEs not listed in the NCI CTCAE, the Investigator should determine the severity of the AE according to the following criteria, as described in Section 8.1.1.1 of the protocol.

- Mild (Grade 1): Asymptomatic or mild symptoms, Events require minimal or no treatment and do not interfere with the participant's daily activities.
- Moderate (Grade 2): Events result in a low level of inconvenience or concern with therapeutic measures. Moderate events may cause some interference with functioning and daily activities.
- Severe (Grade 3): Severe or medically significant but not immediately life threatening, interrupt the participant's daily activities; and may require intervention and hospitalization. Severe events are usually incapacitating.
- Life-threatening (Grade 4): Life-threatening consequences; urgent intervention indicated.

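### SAP 6.5 imputes an incomplete AE start date to before dosing when the AE ended on the dosing day, so that event is classed as not treatment emergent, against the SAP's own principle

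*SAP*

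**What the plan says.** SAP 6.5 opens with a principle for AEs and concomitant medications: "if the missing part of the date causes ambiguity in the temporal relationship to treatment, it will be assumed to be treatment emergent or concomitant".

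Three bullets then give the start-date rules. Each defaults to the dosing date when the recorded part of the date is compatible with it, and each makes an exception that depends on the end date:

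- Day missing, month and year the same as dosing: the dosing day, "unless the end date is on or before the date of study medication administration in which case it will be imputed as the first" day of the end date's month, or the month before if the end date is itself the 1st.
- Day and month missing, year the same as dosing: the dosing day and month, with the same exception, "in which case it will be imputed as 01JAN of the year the end date was reported, or 01DEC of the year prior" where the AE ended on 1 January.
- Date wholly missing: the dosing date, with the same exception, "in which case the missing date will be imputed as 01JAN of the same year as the end date was reported", and again 01DEC of the previous year if the end date is 1 January.

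SAP 6.5 adds that listings show dates as reported, while "the imputed dates will be used for derivations only, such as study day and treatment-emergence status".

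SAP 9.3 defines a TEAE by day: an event that starts or worsens on the dosing day or later. It then says that "AEs recorded in the eCRF which began prior to treatment will not be included in the summary tables", although those events remain in Listing 9.

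On collection, Protocol 8.1 assesses safety from "Adverse Events occurring from the time of the first study product administration (Visit 01A) through Visit 02". Protocol 8.1.1 sends conditions present at screening to medical history unless they worsen.

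**The concern.** An AE that ended on the dosing day and whose start date is incomplete could have begun after the dose. Its timing is ambiguous in the sense of SAP 6.5, and the principle there says to count it as treatment emergent. The bullets do the opposite, because they handle an end date equal to the dosing date in the same way as an end date before it.

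The study gives one dose, so a short-lived event on Day 1 is a plausible form of acute reaction. For events that end on that day, this branch can only take them out of the TEAE counts and never add them. With six participants per group, one misclassified event can visibly change a reported incidence.

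**Working it through.** The plan states no figure here, so the check is to run the rule.

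**Notation.** D is the dosing date, E the AE end date and s the imputed start date. By SAP 9.3 the event is a TEAE if s ≥ D. The case of interest is E = D with a recorded start (if any) compatible with D.

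**Rule as written (exception when E ≤ D), with E = D**

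| Missing part of start | s | Is s ≥ D? |
|---|---|---|
| Day | 1st of the month of D; if D is the 1st, the month before | Never |
| Day and month | 01JAN of the year of D; if D is 1 January, 01DEC of the year before | Never |
| Whole date | As the row above | Never |

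The only dates on which s could have equalled D (the 1st of a month, or 1 January) are the ones that the fallback clauses move back further. The result therefore holds for every dosing date. Running the rule over all 365 + 366 = 731 dates of 2023 and 2024, chosen only as examples, gave 0 of 731 TEAE flags in each of the three branches.

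**Worked example, D = 15 March 2024**

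| Missing part | E = 15 March | E = 16 March |
|---|---|---|
| Day | 1 March, not a TEAE | 15 March, TEAE |
| Day and month | 1 January, not a TEAE | 15 March, TEAE |
| Whole date | 1 January, not a TEAE | 15 March, TEAE |

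One day's difference in the end date reverses the classification.

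**By-product.** With E = D, the fallback clauses also override what was recorded. The imputed month contradicts the recorded start month when D is the 1st (2 × 12 = 24 of 731 dates), and the imputed year contradicts the recorded year when D is 1 January (2 of 731).

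**Rule with *before* (exception when E < D).** With E = D, s = D in every branch: 731 of 731 dates are flagged TEAE in each, and none contradicts a recorded month or year. An AE that ended the day before (E = 14 March) is still imputed to 1 March or 1 January, so the change does not pull in events that were clearly over before dosing.

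**Against the definitions.** SAP 9.3 counts the dosing day itself, so a start on Day 1 is a TEAE whatever the hour. SAP 3.3 words the definition as after administration rather than by day. Under that wording the event is still ambiguous, and the principle in SAP 6.5 decides it the same way.

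**Size per case.** One participant wrongly left out, with no other TEAE in that row:

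- Impairment group of 6 (Protocol 10.2, SAP 5): 1/6 = 16.7 percentage points.
- Pooled matched controls if Part B is run, 6 + 6 + 6 = 18: 1/18 = 5.6 points.

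**The case against.** The strongest case on the other side is that this hardly ever happens. Participants are admitted 12 to 24 hours before dosing and stay to 48 hours (Protocol 6.1.3 and 6.2). AEs are recorded at dosing and at every post-dose time point. The onset date is a collected field (Protocol 8.1.1), missing data are queried (Protocol 12), and SAP 6.5 itself expects little missing data. Safety is descriptive, and the halting rules in Protocol 8.6.1 do not rest on the TEAE tables. All of this stands and limits the expected effect. It does not make the rule right in the cases for which it was written.

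Four stronger readings are tempting, and the documents do not support them.

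- *All reactions that begin and resolve on Day 1 are lost.* No. A Day 1 AE with a complete start date remains a TEAE. Only incomplete start dates are affected. A recorded start month or year earlier than dosing is rightly placed before dosing.
- *An AE that ended on Day 1 can only have started on Day 1.* This is likely, given when AEs are collected, but SAP 9.3 expressly allows for AEs in the eCRF that began before treatment.
- *The events drop out of the secondary safety endpoint.* Not shown. The endpoint in Protocol 3.3.2 and SAP 3.2.2 counts participants reporting AEs, not TEAEs. The overall summary (shell Table 16) has an any-AE row apart from the TEAE rows, and Listing 9 keeps every event. The note to shell Table 17 says that it takes in all AEs collected, so its handling is unclear. The exclusion in SAP 9.3 sits awkwardly with the any-AE row, but what is established is loss from the TEAE rows and tables.
- *Headache (31.5%) and nausea (11.8%) are the events at risk.* Protocol 2.1.5.1 pools single and multiple dosing and gives no onset or resolution times, so those rates do not show how many events start and stop on Day 1.

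One further objection changes the remedy. The same bullets govern concomitant medications, which are collected from 30 days before (Protocol 7.1.1). A blanket change would make a medicine with an unknown start that was stopped on the dosing day appear to start at dosing.

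**Conclusion.** The concern holds in a narrow form. The rule in SAP 6.5 gives the wrong classification for an AE that meets two conditions together: a start date that is missing, or partial but compatible with the dosing month or year, and an end date equal to the dosing date. Such an event is made non-treatment-emergent for every possible dosing date, contrary to the principle that ambiguity "causes ambiguity in the temporal relationship to treatment, it will be assumed to be treatment emergent or concomitant" and to the day-level definition in SAP 9.3. The direction is anti-conservative.

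The size is 16.7 points for one participant in an impairment group of six, or 5.6 points in 18 pooled controls. Both are ceilings for one case. They assume that the participant has no other TEAE in the row and that the safety population has the planned size. If Part B is not run, there are six controls and 1/6 applies to them too. The documents give no frequency for incomplete start dates, and cases should be rare. This is a drafting error of small expected effect, worth correcting because a programmer who follows the text literally will reproduce it.

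**What to change.** In SAP 6.5, for AEs only, change *on or before* to *before* the date of study medication administration in each of the three start-date bullets. Add one sentence: an AE whose incomplete start date is compatible with the dosing day, and whose end date is the dosing date, has its start imputed as the dosing date and is flagged treatment emergent.

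State that the existing wording continues to apply to concomitant medications. No time of day needs to be imputed, because treatment emergence in SAP 9.3 is decided by date.

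The cost is one phrase in three bullets, one sentence separating AEs from medications, and the matching line in the derivation program. No new data are needed, and AEs that ended before the dosing day are handled as now.
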